CHG will be safe for use in a sample of infants 36 weeks PMA or older, and less than 2 months of age (48 weeks PMA) with a CVC as evidenced by an adverse event rate less than 10%.

Research Question 2:

Does twice weekly CHG baths lead to rising (cumulative) CHG blood levels, liver function tests (LFTs -AST/ALT) and Serum Creatinine over time in a sample of infants 36 weeks PMA or older, and less than 2 months of age (48 weeks PMA) with a CVC?

Hypothesis 2:

Twice weekly CHG baths do not lead to rising (cumulative) CHG blood levels, LFTs (AST/ALT)

and Serum Creatinine over time in a sample of infants 36 weeks PMA or older, and less than 2 months of age (48 weeks PMA) with a CVC.

Methods

Study Design: A pilot study using a single arm trial design.

Study Sample: Our convenience sample will include 50 infants. Infants admitted to the NICU or pediatric CICU will be eligible to participate.

Inclusion criteria.

- Greater than/equal to 36 weeks PMA (gestational age + chronological age)
- Less than/equal to 48 weeks PMA (gestational age + chronological age)
- Greater than/equal to 3 days of age
- Existing or soon to be placed, peripheral or surgical CVC
- Permission to participate in trial by attending physician
- Parent or legal guardian informed consent to participate in the trial

Exclusion criteria.

- Infant with a large open lesion or severe skin condition (i.e., Myelomeningocele, Gastroschisis, lymphatic malformation, open chest, ostomies and/or mucus fistulas or Icthyosis)
- Infants with active seizure disorders
- Infants with Hypoxic Ischemic Encephalopathy
- Infants with severe multi-system organ failure or Liver failure as defined by documentation of abnormal liver function tests: alanine aminotransferase (ALT) and aspartate aminotransferase (AST) Gamma-glutamyltransferase (GGT) and L-lactate dehydrogenase (LD).
- HCT \leq 28%: Respiratory support (mechanical ventilation, continuous positive airway pressure or high flow nasal cannula with FiO₂ > 25% Oxygen by nasal cannula > 1 liter/min) or HCT \leq 25%: No respiratory support.
- Infant with renal impairment as defined by: documented serum Creatinine greater than 0.7, renal disorders (renal agenesis, polycystic kidney disease, dysplastic kidneys, acute renal injury).
- Infants deemed clinically unstable by their physician such as patients that are extremely fragile and wouldn't tolerate the stimulation of the bathing process or those infants being considered for withdrawal of care.

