Random observations of CHG baths will be performed throughout the entire study period by a designated clinician to ensure that all nurses are bathing the infants using the same technique. Each study team member actively bathing study subjects will be audited a minimum of once every two months. These observations will be documented on the CHG Bath Audit Tool (Appendix K) and scores of 15/15 points are acceptable. Any score lower than 15 will require retraining on the bathing technique. Also to facilitate reliable assessment of skin lesions, a CHG Erythema Assessment Tool (Appendix L) will be available for nurses to follow during their assessments (maintained at each study patients' bedside) (Figure 1.).

The sponsor-investigator will also engage the services of a qualified independent monitor to ensure the protection of the rights of human subjects, the safety of all subjects involved in the investigation and the quality and integrity of the data resulting from the trial. The independent monitor will conduct a pre-monitoring set-up visit and a monitoring visit after every fifth patient has been recruited and on the study for 1 week.

Data Analysis. With the support of a faculty statistician from the BCH Center for Patient Safety and Quality Research, we will use descriptive statistics including mean, median, range, and frequencies to describe the study sample and the findings (skin findings and adverse events). We will characterize the study sample on demographic and clinical characteristics. Our primary outcome measures will be proportion of subjects that experience any adverse event, and the rate of adverse events per 100 patient-days of follow-up. Our inferential statistics will calculate 95% confidence intervals around these estimates.

Research Question 1:

Are twice weekly CHG baths safe for use in a sample of infants 36 weeks PMA or older, and less than 2 months of age (48 weeks PMA) with a CVC?

Data Analysis 1:

Descriptive statistics including mean, median, range and frequencies will be used to describe adverse events (including skin reactions and other untoward events). We will characterize the demographic and clinical characteristics of subjects that experience adverse events, although we will not perform hypothesis tests of association. We will consider time-to-rash data using Kaplan-Meier estimators.

Research Question 2:

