Holding rules for patients with anemia requiring blood transfusion. All study participants that require a blood transfusion while enrolled in the study will have CHG baths suspended until 1-week post transfusion and will have a pre- and post-transfusion assessment of vital signs (ranges-heart rate, respiratory rate, blood pressure, oxygenation requirement and means of respiratory support). A post-transfusion hematocrit will also be obtained, if not attained via standard of care, and documented on the CHG Blood Transfusion Tool (Appendix N). The CHG baths will resume 1-week post transfusion if study participant is deemed stable by both the study and medical teams.

Study participants that do not receive a blood transfusion or are deemed not stable will have monitoring of daily vital signs (ranges-heart rate, respiratory rate, blood pressure, oxygenation requirement and means of respiratory support), HCTs that are obtained as routine ICU care, and significant changes to clinical status for 1 month from cessation of CHG baths or until discharge, whichever comes first to assess for adverse events related to anemia.

Stopping rules for patients with anemia requiring blood transfusion. All study participants that have had CHG baths suspended and that do not receive a blood transfusion or are deemed unstable will be removed from the study after completing the clinical monitoring as described above.

Adverse Event (Other Than Anemia):

Holding rules for patients that experience an adverse event: All study participants that experience an adverse event, as described in table 1, and have CHG baths suspended due to the adverse event will have 2 CHG levels obtained within 1 week of CHG bath (recorded on CHG Lab Work Log), unless the previous level was not detectable. These infants will also have monitoring for adverse event symptom resolution and daily vital signs (ranges-heart rate, respiratory rate, blood pressure, oxygenation requirement and means of respiratory support) for 1 month from cessation of CHG baths or until discharge, whichever comes first.

Stopping rules for patients that experience an adverse event. All study participants that have CHG baths suspended due to an adverse event will be removed from the study after completing the clinical monitoring as described above.

Clinical Instability:

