AST >70 u/l	Discontinue CHG baths	Adverse Event (Other Than Anemia)	Immediately reportable to PI; meet with DSMC
ALT >60 u/l	Discontinue CHG baths	Adverse Event (Other Than Anemia)	Immediately reportable to PI; meet with DSMC
Serum Creatinine 0.7 mg/dl or greater	Discontinue CHG baths	Adverse Event (Other Than Anemia)	Immediately reportable to PI; meet with DSMC
HCT <= 28%: Respiratory support (mechanical ventilation, continuous positive airway pressure or high flow nasal cannula with FiO ₂ > 25% Oxygen by nasal cannula > 1 liter/min) HCT <= 25%: No respiratory support	Discontinue CHG baths	Anemia/Blood Transfusions	Immediately reportable to PI; Discuss with medical team; meet with DSMC
Other			
Clinical Instability	Discontinue CHG baths	Clinical Instability	Immediately reportable to PI; include in monthly DSMP report

Financial Support:

This study is being funded by the Program for Patient Safety and Quality, the Department of Lab Medicine Clinical Chemistry Training Program, and the American Association of Critical Care Nurses. The nursing departments from the participating units will purchase the 2% CHG cloths for this study. The Department of Newborn Medicine will fund all supplemental laboratory specimens.

References:

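### An infant with creatinine of exactly 0.7 may enter, yet 0.7 is a Table 1 adverse event, and no rule requires a lab event to be new since the first bath

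*Combined protocol and SAP*

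**What the plan says.** All references are to the combined protocol and SAP.

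- **Entry, kidney (Exclusion criteria):** "Infant with renal impairment as defined by: documented serum Creatinine greater than 0.7". A value of exactly 0.7 is not excluded. No unit is given; I take mg/dL from Table 1.
- **Entry, liver (Exclusion criteria):** "Liver failure as defined by documentation of abnormal liver function tests", with no numeric limit.
- **Trigger (Table 1, Lab Value Assessment):** "Serum Creatinine 0.7 mg/dl or greater", AST above 70 or ALT above 60. Each discontinues baths under the rules for adverse events other than anemia.
- **Status and consequence (Holding and Stopping Rules):** the holding rule covers "All study participants that experience an adverse event, as described in table 1" with baths suspended. The stopping rule adds that "All study participants that have CHG baths suspended due to an adverse event will be removed from the study" once monitoring is complete.
- **Primary outcome (Data Analysis):** the "proportion of subjects that experience any adverse event", together with a rate per 100 patient-days. Hypothesis 1 regards the baths as safe "as evidenced by an adverse event rate less than 10" percent.
- **Baseline labs:** Human Subjects, item 4, has CHG, AST, ALT and creatinine drawn at baseline. The section on procedures for obtaining levels names only CHG at baseline and puts the other labs on Fridays. The section on iatrogenic anemia budgets 0.5 mL at baseline, the volume of one CHG sample.
- **Hematocrit:** entry and Table 1 use the same limits (for example "HCT <= 25%: No respiratory support"), but no section lists a baseline hematocrit draw.

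**The concern.** The two creatinine limits overlap at 0.7, and the Table 1 limits are absolute values. No section asks whether a lab value was already there before the first bath. Data Collection logs the time of onset from study start, but nothing uses it to decide whether an event counts.

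This is a single-arm study, so no control group shows how many infants carry such values anyway. A finding that predates all exposure could be attributed to the baths and set against the 10% criterion, and the infant would lose further bath exposure. The pilot is meant to support a larger efficacy study, so overstating harm has a cost.

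**Working it through.** **1. Cut-offs side by side**

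| Lab | Entry rule | Table 1 trigger | Overlap |
|---|---|---|---|
| Creatinine | excluded if documented >0.7 | ≥0.7 | exactly 0.7: certain |
| AST, ALT | excluded if documented abnormal, no number | >70, >60 | only if abnormal is not read to exclude these values |
| Hematocrit | ≤28% with, ≤25% without respiratory support | same | none in the limits |

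A separate route applies to all four labs: an infant with no value before the first bath. The section on liver and renal function expects some infants whose condition gave no reason to monitor AST, ALT and creatinine. If the procedures section is followed, the first study value comes on Friday, 1 day after a Thursday first bath or 4 days after a Monday one. For AST, ALT and creatinine this route closes if Human Subjects, item 4, is followed. For hematocrit it stays open whenever the chart has no value. A low hematocrit follows the anemia rules, under which baths may resume after a transfusion.

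**2. Effect of one counted infant on the proportion**

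Input: n=50 (Study Sample). Each infant adds 1/50 = 2 percentage points. Clopper-Pearson two-sided 95% upper limits:

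| Events | Estimate | Upper limit |
|---|---|---|
| 0/50 | 0% | 7.1% |
| 1/50 | 2% | 10.6% |
| 2/50 | 4% | 13.7% |
| 5/50 | 10% | 21.8% |

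The plan does not say whether the estimate or the limit is compared with 10%. If the limit, one infant is enough to cross; if the estimate, five reach 10%.

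**3. Effect on meeting the criterion**

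Inputs: 3.5 and 1.0 events per 1000 days over 7 days (Sample Size Justification). The plan's own figures from these inputs, 83% and 40% for at least one event, do not reproduce: 1 − exp(−rate × 350/1000) gives 70.6% and 29.5%, whereas 500 days would give 82.6% and 39.4%. That is a separate matter and this point does not rest on it.

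Per-infant risk of a new event is p = 1 − exp(−rate × 7/1000): 2.42% at 3.5 and 0.70% at 1.0. Let q be the share of infants entering on the event side. The documents give no value, so q is an assumption. Combined risk is 1 − (1 − p)(1 − q), if every such infant is counted. The chance that the estimate stays below 10% is P(at most 4 of 50):

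| q | 0% | 1% | 2% | 5% |
|---|---|---|---|---|
| 3.5 per 1000 | 99.3% | 97.3% | 93.3% | 70.0% |
| 1.0 per 1000 | 100.0% | 99.8% | 98.9% | 84.8% |

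The chance of at least one affected infant, 1 − (1 − q)^50, is 39.5%, 63.6% and 92.3% for q of 1%, 2% and 5%.

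**4. Effect on the rate outcome**

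One event over the planned 350 days adds 1/350 = 2.9 per 1000 days. If follow-up instead matches the 9 to 15 day CICU stay, that is 450 to 750 days, and one event adds 2.2 to 1.3 per 1000.

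**The case against.** - **Lab-only events may not count.** The section on CHG blood levels makes visual and clinical assessment the primary safety measure. AST, ALT and creatinine also have their own research question, about values rising over time, and an unchanged 0.7 is not rising. This stands as a real doubt, but is not decisive: the same section lists liver and renal test abnormalities among adverse reactions, Data Analysis counts any adverse event, and the holding rule points to Table 1. Baths stop either way.
- **The certain overlap is one value.** This stands. The AST/ALT and missing-value cases are conditional, and other exclusions or physician judgment may remove some infants at 0.7.
- **The size is assumed.** This stands. Follow-up length matters as well: at 3.5 per 1000 over 15 days, the chance of at most 4/50 is already 89% with no overlap at all.
- **The DSMC reviews these triggers, and onset is logged.** That helps where a baseline value exists, but gives no rule for counting.

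A reader might go further and infer that affected infants drop out of the 50. The documents do not support this: removal follows monitoring of up to a month, and nothing takes the infant out of the denominator. A reader might also infer from the matching limits that hematocrit is safe from the problem. It is not, because no baseline hematocrit is scheduled.

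**Conclusion.** The point holds and should be fixed. The mismatch at exactly 0.7 and the absence of any new-since-first-bath condition can be read directly from the text. The extension to AST and ALT depends on how the liver exclusion is read, and the extension to any lab depends on there being no value before the first bath.

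The number of infants affected is unknown. On the assumed shares, and only if lab events count in the primary proportion, the effect on the point estimate is small below about 2% of infants and clear at 5%. If the upper confidence limit is what is compared with 10%, a single counted infant can decide the result when nothing else occurs.

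The bias runs towards overstating harm. It would be wrong to infer that the plan hides harm through this gap, or that the 10% criterion is bound to fail.

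**What to change.** 1. Change the renal exclusion to creatinine of 0.7 mg/dL or greater, so that it meets Table 1 without overlap.
2. Bring the procedures and blood-volume sections into line with Human Subjects, item 4, and add hematocrit. AST, ALT, creatinine and hematocrit should be available before the first bath, from the chart where possible and otherwise from a baseline draw.
3. State that a lab value counts in the primary outcome only if it crosses its Table 1 limit after the first bath from a baseline on the non-event side. Leave Table 1 safety management unchanged.

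Numeric AST and ALT exclusions are optional, since the counting rule already prevents the miscount.

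**Cost:** protocol wording, possibly a few infants no longer eligible, and up to 1.0 mL more blood at baseline (0.5 mL for AST, ALT and creatinine; 0.5 mL for hematocrit) where the chart has no values. On the plan's own volumes the 12-week maximum goes from 0.5 + 12 × 1.5 = 18.5 mL (stated as 18) to 1.5 + 12 × 1.5 = 19.5 mL. Against its 224 mL blood volume for a 2.8 kg infant, that is 8.3% to 8.7%. The stated total should be updated accordingly.

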- Rub area to be cleansed with a back and forth motion
- Use 1 cloth for neck, arms, and legs (stopping at ankles to prevent wiping of feet/heels)
- Use second cloth for torso and back

CHG Bath Intervention. Subjects whose parents consent for this study will receive a CHG bath twice weekly. The CHG baths will be performed by 1 of 5 trained study nurses on each unit to ensure a standard bathing technique. Baths will be performed every Monday and Thursday during the day shift, for up to 12 weeks post enrollment or until the CVC is removed or the patient is discharged. Nurses will use pre-warmed 2% CHG impregnated non-sterile cloths from Sage Products Inc. CHG bath cloths will be pre-warmed to 100°F (37.8°C) in the warmers provided by Sage Products Inc. Baths will entail cleaning the infants with 2 CHG bathing cloths (1 package) beginning at the neck, working down the body toward the feet. Nurses will be instructed not to use the CHG cloths on the face, scalp, or over open body orifices or wounds, including the genitalia and anus (where bloodstream absorption is enhanced). The genital and anal areas will be protected by placing a clean diaper on the study subject prior to initiation of CHG bath. Cleansing of the feet/heels with CHG will be avoided due to the possibility of blood sample contamination as explained by Cowen et al (1979). Nurses will document completion of the CHG baths on the CHG Bath Data Collection Tool that will be kept at each participant's bedside. When a bath needs to be delayed for clinical reasons, it will be done as close to the scheduled time as possible.

Cleansing between CHG baths: Cleansing of infants between CHG baths may be required if they become soiled. These baths or partial baths will be done per NICU standard of care using (non-CHG) Comfort Cloths by Sage Products Inc. and documented on the CHG Exposure and Comfort Cloth Bath Log (Appendix C).

CHG Exposure: Infant participants have the potential for additional CHG exposures for central line insertions, dressing changes, and perioperative bathing. Additional CHG exposures will be recorded on the CHG Exposure and Comfort Cloth Bath Log.

Monitoring for Adverse Events

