Assessment of Liver and Renal Function. Most drugs or chemicals are excreted from the body via the hepatic or renal systems. Therefore, standard LFTs, namely AST and ALT, and the Serum Creatinine levels will be monitored on all subjects. If these labs have been obtained as part of the standard of care, the results will be used by the study team and not repeated in order to minimize additional blood loss or iatrogenic anemia. However, if the study subject's diagnosis did not warrant monitoring of these labs, they will be obtained weekly with the CHG blood level.

Procedures for Obtaining CHG, ALT, AST and HCT levels. A single CHG level will be obtained at baseline and then weekly on Fridays for the remainder of the study for each study participant. Every Friday additional labs will be obtained to monitor liver and renal function (AST, ALT, Serum Creatinine) and HCT for anemia.

Often these lab values are obtained as part of routine care in the ICU. If these labs have not been obtained, they will be added to the weekly labs that will require an additional 1.0 mLs. The study personnel performing the bath will assess the need for the additional labs and notify the bedside nurse so that these labs can be obtained at the appropriate time as per the CHG Study Research Order (Appendix F). The study labs will be drawn with other lab work via central line whenever possible. If no other lab work is scheduled to be obtained, or if the central line gauge is too small (less than 2.6 Fr), then the labs will be obtained at the designated time by heel stick. When no other lab work is to be obtained, infants will need 1-2 heel sticks per week for a required sample of 1- 1.5 mLs in order to limit access of CVC and minimize risk of infection. Standard heel sticks are safely performed on patient care units using the lateral aspect of the infants' pre-warmed heel. Blood levels will be recorded on the CHG Lab Work Log (Appendix G) and entered into a computerized database. Lab specimens for this study will be tracked by utilizing a CHG Study Lab Requisition Form (Appendix H) that bears the patients study ID number followed by a unique specimen identifier (i.e. Patient ID "#CHG001" followed by unique lab identifier "3456").

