Does twice weekly CHG baths lead to rising (cumulative) CHG blood levels, liver function tests (LFTs -AST/ALT) and Serum Creatinine over time in a sample of infants 36 weeks PMA or older, and less than 2 months of age (48 weeks PMA) with a CVC?

Data Analysis 2:

Descriptive statistics including mean, median, range and frequencies will be used to describe CHG, LFTs and serum Creatinine blood levels over time. We will examine scatterplots and other graphical analysis of blood level dispersion over time to look for relationships.

Sample Size Justification. The primary quantitative goal of this study is estimation of the adverse event rate per 100 patient days. The study sample size will impact the precision of this estimate, and we will establish an upper bound on the rate if zero adverse events occur. In this context, we designed the study sample to expand the existing knowledge base.

Based on recent safety data (Quach, et al 2014) on roughly 200 neonates which recorded no adverse events, we assume the rate of adverse events using CHG bath is lower than 5 events per 1000 days of post-exposure follow-up. We propose following N=50 subjects over 7 days of post-exposure follow-up, for a total of 350 observation days. Assuming rates of 3.5 events or 1.0 events per 1000 days of follow-up, the probability that at least one subject will experience an adverse event is roughly 83% or 40% respectively. Using Monte Carlo simulations, the mean upper bound for estimable rates is 5.5 events per 1000 days.

Auditing and Inspecting:

The sponsor-investigator will permit study-related monitoring, audits, and inspections by the Boston Children's Hospital IRB, the independent data monitor and government regulatory bodies, of all study related documents (e.g. source documents, regulatory documents, data collection instruments, study data etc.). The Investigator will ensure the capability for inspections of applicable study-related facilities.

Human Subjects:

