Holding rules for patients that become clinically unstable. For the safety of the study participant bathing will be suspended for infants demonstrating significant or acute impairment of their clinical status as indicated by their medical team. For example, patients requiring volume resuscitation due to blood and fluid losses, or a patient in the immediate post-operative period will not be bathed until return to baseline stability. These patients will have 2 CHG levels obtained within 1 week of last CHG bath, unless previous level was non-detectable. Infants deemed not appropriate for participation by either the study team or medical team will have monitoring of daily vital signs (ranges-heart rate, respiratory rate, blood pressure, oxygenation requirement and means of respiratory support) for 1 month from cessation of CHG baths or until discharge, whichever comes first.

Stopping rules for subjects that become clinically unstable. Study subjects whose clinical status does not return to baseline, as assessed by both the study and medical teams will be removed from the study after completing the clinical monitoring for 1 month as described above.

Table 1: Management of Adverse Events to CHG Baths

Erythema Assessment (see CHG Erythema Assessment Tool for visual comparisons)			
Finding	Action	Follow Holding and Stopping Rules	Reporting
1. Mild redness X1	None	Not Applicable	No immediate action; Send email update to PI; include in monthly DSMP report
2. Mild redness X2, persistent redness leading up to 2 nd bath, or moderate redness:	Discontinue CHG baths (unless rash is limited only to diaper area)	Adverse Event (Other Than Anemia)	Immediately reportable to PI; include in monthly DSMP report
3. Raised rash	Discontinue CHG baths (unless rash is limited only to diaper area)	Adverse Event (Other Than Anemia)	Immediately reportable to PI; include in monthly DSMP report
4. Blister(s)	Discontinue CHG baths	Adverse Event (Other Than Anemia)	Immediately reportable to PI; meet with DSMC
5. Open area(s)	Discontinue CHG baths	Adverse Event (Other Than Anemia)	Immediately reportable to PI; meet with DSMC

6. Evidence of systemic event	Discontinue CHG baths	Adverse Event (Other Than Anemia)	Immediately reportable to PI; meet with DSMC
7. Anaphylaxis	Discontinue CHG baths	Adverse Event (Other Than Anemia)	Immediately reportable to PI; meet with DSMC
Lab Value Assessment			

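### CHG draws stay on Fridays while baths are delayed, held or suspended, so Data Analysis 2 mixes accumulation with time since exposure

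*Combined protocol and SAP*

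**What the plan says.** - **Baths.** Monday and Thursday, day shift. Under CHG Bath Intervention: "When a bath needs to be delayed for clinical reasons, it will be done as close to the scheduled time as possible". No window in hours is given.
- **CHG draws.** The section on procedures for obtaining blood levels sets the sampling rule: "A single CHG level will be obtained at baseline and then weekly on Fridays for the remainder of the study for each study participant". The draw is tied to a weekday, not to a bath.
- **Transfusion.** Under Anemia/Blood Transfusions, affected infants "will have CHG baths suspended until 1-week post transfusion". No matching rule pauses or moves the Friday level.
- **Adverse event.** Infants whose baths are suspended "will have 2 CHG levels obtained within 1 week of CHG bath", except where the preceding level was undetectable.
- **Clinical instability.** The hold has no fixed length; for example, "a patient in the immediate post-operative period will not be bathed until return to baseline stability". Sampling after such a hold is also laid down in that section: "These patients will have 2 CHG levels obtained within 1 week of last CHG bath, unless previous level was non-detectable".
- **Analysis.** Data Analysis 2 summarises CHG over time by mean, median, range and frequencies, and adds: "We will examine scatterplots and other graphical analysis of blood level dispersion over time to look for relationships". It does not index, stratify or restrict by time since the last bath or other exposure.
- **Hypothesis.** Hypothesis 2 is a no-rise statement: "Twice weekly CHG baths do not lead to rising (cumulative) CHG blood levels".

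**The concern.** A blood level reflects both what has built up over earlier baths and how long ago the last exposure was. Research Question 2 is about the first. If the interval from exposure to draw were constant, a description by study week would isolate it. Here the interval can change from week to week within an infant and between infants, and the planned description does not take this into account. A low Friday level may mean no accumulation or a missed Thursday bath; a jump the following week may mean accumulation or a return to schedule.

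This matters because Hypothesis 2 will be judged from these summaries and plots alone, with no model that could adjust for timing. The CHG blood levels section also says that the sensitive assay should help in understanding absorption and elimination, which requires each level to be tied to an exposure. Off-schedule weeks are foreseeable: the CICU enrols infants having cardiac surgery, and the protocol writes its own rules for transfusion, instability and the post-operative period.

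**Working it through.** The plan states no bath-to-draw interval, so there is no figure of its own to reproduce.

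**Step 1: the calendar.** Inputs: baths Monday and Thursday; draw Friday; transfusion hold 7 days (168 h). Assumption: baths and draws at the same clock time. Interval = draw time minus time of the last study bath given before it.

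- On schedule, Thursday to Friday: 24 h. If bath and draw can each fall anywhere in an assumed 07:00–19:00 shift, 12 to 36 h.
- Monday bath one day late: still 24 h.
- Thursday bath moved to Friday before the draw: under 24 h.
- Thursday bath missed or given after the Friday draw, Monday to Friday: 4 × 24 = 96 h.
- Transfusion hold that removes the next Monday and Thursday baths, Thursday to Friday of the following week: 8 × 24 = 192 h.
- Over the 168 possible start hours of a one-week hold, the longest interval is 192 h for 96 and 96 h for 72, if any bath falling inside the 168 h is missed. If the hold is counted in calendar days and the seventh day is allowed, a Thursday transfusion after that day's bath leaves the interval at 24 h.
- Two-week instability hold starting after a Friday draw: 192 + 168 = 360 h.
- Extra levels after an adverse-event or instability suspension: up to 168 h.

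**Step 2: illustration of the effect on levels.** The documents give no half-life h, so 24, 48, 96 and 168 h are assumed, with equal input per bath and no other CHG. Level at time t = sum over baths given of 2^(−(t − bath time)/h), with baths at hours 0 and 72 of each week and the draw at hour 96. All results are divided by the on-schedule week-1 level.

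Example, h = 48:
- Week 1 on schedule: 2^(−96/48) + 2^(−24/48) = 0.250 + 0.707 = 0.957.
- Each earlier week carries over by 2^(−168/48) = 0.0884, so week 4 on schedule = 0.957 × (1 + 0.0884 + 0.0078 + 0.0007) = 1.050; ratio 1.10.
- Week 4, Thursday bath after the draw: (1.050 − 0.707)/0.957 = 0.36.
- Week 4, both baths held: (1.050 − 0.957)/0.957 = 0.10.
- Week 1, Thursday bath after the draw: 0.250/0.957 = 0.261. An on-schedule week 4 compared with it gives 1.097/0.261 = 4.2.

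| Half-life (h) | Week 4 on schedule | Week 4, Thursday bath after draw (96 h) | Week 4, both baths held (192 h) | Week 4 on schedule ÷ week 1 delayed |
|---|---|---|---|---|
| 24 | 1.01 | 0.12 | 0.01 | 9.1 |
| 48 | 1.10 | 0.36 | 0.10 | 4.2 |
| 96 | 1.41 | 0.79 | 0.41 | 3.8 |
| 168 | 1.88 | 1.30 | 0.88 | 4.4 |

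In a single infant, a delayed or held week 4 can turn a rise into an apparent fall, and a delayed week 1 can create or exaggerate a rise.

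**Step 3: group means.** Assume 10% of infants are off schedule in the stated week; the true share is not given. Ratios are for h = 24, 48, 96, 168.

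- 10% delayed in both weeks, (0.9 × week 4 on + 0.1 × week 4 delayed) ÷ (0.9 + 0.1 × week 1 delayed): 1.01, 1.10, 1.44, 1.93. For h = 48: (0.9 × 1.097 + 0.1 × 0.358)/(0.9 + 0.1 × 0.261) = 1.10. This is essentially the on-schedule ratio, or slightly above it.
- 10% delayed in week 4 only, 0.9 × week 4 on + 0.1 × week 4 delayed: 0.92, 1.02, 1.35, 1.82.
- 10% held in week 4 only. The held level is the on-schedule level minus 1, so the ratio falls by 0.1 × 1 = 0.10: 0.91, 1.00, 1.31, 1.78.

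The Sample Size Justification plans on 7 days of follow-up, about one Friday level per infant. Week-4 comparisons therefore concern only infants who stay longer.

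**The case against.** The strongest reply is that this is a descriptive second question in a pilot, using a research-only assay, with no pooled trend test to bias. Data Analysis 2 leaves room for further graphs. Bath labels are dated, other CHG exposures are logged and levels are recorded, so the analyst could derive the interval at any time. The draw time may also be set in Appendix F, which is not in the text available. Most of this stands. Nothing is lost from the data; what is missing is any statement that the interval will be used. Choosing how to use it after seeing the levels is weaker than stating it beforehand, and the body of the protocol fixes the Friday whatever Appendix F says about the hour.

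A reader might go further and infer that off-schedule levels systematically favour Hypothesis 2 and would hide a real rise. The documents do not support that. No section says that delays cluster late; equal delays in weeks 1 and 4 leave the group ratio almost unchanged, and an early delay inflates it. The dramatic falls in the table are single infants under assumed half-lives. Nor is a level long after a study bath necessarily long after CHG: the CHG Exposure paragraph allows for line placement, dressing changes and bathing around surgery, and infants held post-operatively are the likeliest to have had the last of these.

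**Conclusion.** The confounding is real and follows from the text: bath timing varies, draw timing does not, and the planned description ignores the gap. Nominal intervals are 24, 96 and 192 h, with shorter and longer ones possible. The 192 h figure assumes that Friday draws continue through a transfusion hold, which the draw rule implies and nothing contradicts.

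The distortion from delayed baths can go either way. Only hold and post-suspension levels have an expected direction: they arise after bathing has begun and tend to lower later points, provided there was no other CHG exposure. The net size cannot be stated without a half-life and a frequency of delays and holds; the ratios above show what is possible, not what is likely.

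It would also be too much to infer that the primary safety result is compromised. The primary outcomes are adverse-event measures, and CHG levels are kept out of individual clinical decisions. The point concerns the interpretation of Research Question 2 and is worth settling before the levels are analysed.

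**What to change.** In Data Analysis 2, keep the summary of all CHG levels and add:

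- (a) a description over time of baseline plus the weekly levels drawn on the day after a study bath; and
- (b) a plot of every level against days since the last recorded CHG exposure, whether a study bath or any exposure on the Appendix C log, with levels from delayed, held and suspended periods marked.

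The clock in (b) should be the last CHG exposure of any kind, not the last study bath; otherwise a level taken the day after a perioperative CHG bath would be shown as many days off CHG.

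The cost is a few sentences and one extra plot. No draw moves, no level is discarded, and no blood or form is added. The drawback is that (a) rests on fewer levels, weighted to infants stable enough to stay on schedule. In a safety study that selection matters, which is why the all-levels summary must stay beside it.
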